**8.3.7****Adverse Events of Special Interest**

Not applicable.

**8.4****Treatment of Overdose**

Not applicable.

**8.5****Pharmacokinetics**

Not applicable.

**8.6****Pharmacodynamics**

[figure not shown]
Not applicable.

Substance code: N/A

Cognition and HRQoL in adults with highly active RMS in Year 3 and  
4 after initial Mavenclad® dose

MS700568\_0158

CCI

CCI

## 8.9 Immunogenicity Assessments

Not applicable.

## 9 Statistical Considerations

The statistical analyses described in this section will be performed as further outlined in the Integrated Analysis Plan (IAP), which will be finalized prior to database lock and will be included in the CSR for this protocol.

Study data will be integrated with study data from the CLARIFY MS trial as required to perform the statistical analyses.

Continuous variables will be summarized using descriptive statistics, i.e., number of participants, number of participants with missing and non-missing values, mean, standard deviation, median, 25th Percentile, 75th Percentile (Q1-Q3), minimum, and maximum. Qualitative variables will be summarized by counts and percentages.

CCI

### 9.3 Populations for Analyses

The analysis population are specified in [Table 5](#). The final decision to exclude participants from any analysis population will be made prior to database lock.

**Table 5** Analysis Populations

Analysis Set	Description
Screening Set	All participants who provided informed consent for the extension study
Full Analysis Set (FAS)	The FAS will include all eligible participants
Safety Analysis Population	The Safety Analysis Set will include all participants from the Screening Set who received at least one dose of cladribine tablets

FAS=Full analysis set.

The efficacy analyses will be performed on the Full Analysis Set (FAS). All safety analyses will be performed on the Safety Analysis Population.

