**MS700568\_0158**

---

HRQoL=Health related quality of life; SDMT=Symbol Digit Modalities Test; MSQoL-54=Multiple Sclerosis Quality of Life 54 Questionnaire; RMS=Relapsing Multiple Sclerosis.

**Overall Design:** This is the extension study to the 2-year CLARIFY MS trial to observe participants during the third and fourth year after the initial cladribine tablet dose; no cladribine tablets will be administered during the extension study period. At the extension study Baseline, data will be collected retrospectively from the potential transition gap period between the CLARIFY MS trial and CLARIFY MS Extension study (i.e., between M24 and extension study Baseline). In addition, participants will attend visits for assessments at the extension study Baseline (planned to coincide with or be as near to M24 as possible to minimize the transition gap period), M36 at 36 months/3 years after initial dose of cladribine tablets, and M48 at 48 months/4 years after initial dose of cladribine tablets.

**Disclosure Statement:** This will be an open label, single arm, exploratory, multicenter, retrospective and prospective, 2-year Phase IV study. The purpose of the study is the evaluation of the effect of a treatment for highly-active RMS.

**Number of Arms:** 1

**Blinding:** Not applicable

**Number of Participants:** Depending on the drop-out rate of the parent study, it is expected that up to a maximum of 380 participants will be enrolled into the extension study. Assuming a drop-out rate over the course of the extension study of 10% to 20%, it is expected to achieve a maximum of 300 to 340 evaluable participants for the extension study.

**Study Intervention Groups and Duration:** The extension study will cover a 2-year period in which the participants will not be treated with cladribine tablets, which were administered in the CLARIFY MS trial.

[figure not shown]

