## 5.1 Inclusion Criteria

Participants are eligible to be included in the study only if all the following criteria apply:

1. Participants having participated in the CLARIFY MS trial, who
  - a. Have at least CLARIFY MS Baseline data on SDMT
  - b. Received at least a single dose of cladribine tablets in the CLARIFY MS trial
  - c. Completed the Final Study Visit (M24) of the CLARIFY MS trial.
2. Capable of giving signed informed consent, as indicated in [Appendix 2](#), which includes compliance with the requirements and restrictions listed in the informed consent form (ICF) and this protocol.

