### Prior/Concurrent Clinical Study Experience

2. Participation in other studies/trials.

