## 5.4 Screen Failures

Individuals who do not meet the criteria for participation in this study (screen failure) may not be rescreened.

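### The Safety Analysis Population in Table 5 keeps dosed screen failures in the AE denominator, because its dose condition refers to treatment given only in the parent trial

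*Protocol*

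**What the plan says.** Table 5 in Protocol Section 9.3 defines three sets. The Screening Set is "All participants who provided informed consent for the extension study". The Full Analysis Set is narrower: "The FAS will include all eligible participants". The safety set is built from the Screening Set, not the FAS: "The Safety Analysis Set will include all participants from the Screening Set who received at least one dose of cladribine tablets". Its use is fixed in the same section: "All safety analyses will be performed on the Safety Analysis Population".

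Four other places matter:

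- Section 1.1 (Overall Design) says that "no cladribine tablets will be administered during the extension study period".
- Section 5.1 already makes a parent-trial dose an entry condition, criterion 1b: "Received at least a single dose of cladribine tablets in the CLARIFY MS trial".
- Section 5.4 foresees screen failures: "Individuals who do not meet the criteria for participation in this study (screen failure) may not be rescreened".
- Section 8.3.1 starts AE collection at consent. It also has events between parent-trial exit and consent recorded retrospectively once consent is given.

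**The concern.** In a trial that administers treatment, requiring a first dose does useful work: screen failures are never dosed, so they drop out of the safety set. Here every study dose was taken in CLARIFY MS, before anyone could consent to the extension. The condition therefore removes only a consenting person who was never dosed in the parent trial, and inclusion criterion 1b covers that case already. Someone who was dosed, consents and then fails another criterion, for example exclusion 2 ("Participation in other studies/trials"), is outside the FAS but inside the safety set.

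The safety endpoint in Table 3 is the occurrence of AEs and SAEs over years 3 and 4, and Section 9 summarises qualitative variables by counts and percentages. A person who does not go on to M36 or M48 adds one to the denominator but can supply only the events known at Baseline. The percentages are then diluted, and the safety population is larger than the population observed over the two years.

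**Working it through.** **Set logic.** Take a person dosed in CLARIFY MS who consents to the extension and then fails exclusion 1 or 2.

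| Set | Condition | In the set? |
|---|---|---|
| Screening Set | consented | yes |
| Safety Analysis Population | Screening Set and dosed | yes |
| FAS | eligible | no |

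No further condition in Table 5 removes this person from the safety set.

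**What such a person can contribute.** By the wording of Section 5.4, a screen failure does not meet the criteria for participation, and the protocol schedules no M36 or M48 visit for such a person. Gap events can be recorded. Table 2 allows Baseline anywhere between M24 and M36, so the gap can run from 0 to about 12 months, at most half of the two-year endpoint period. Section 4.1 plans Baseline as near to M24 as possible, so the usual gap should be short.

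**The plan's own size figures.** Section 1.1 gives a maximum of 380 enrolled, 10% to 20% drop-out and 300 to 340 evaluable. 380 × 0.90 = 342 and 380 × 0.80 = 304, which agree with the stated figures after rounding. The point does not depend on them.

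**Size of the dilution.** The protocol gives neither a screen-failure number nor an AE rate, so both are assumed.

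- N = 380 consented. Sections 6.5 and 8.3.1 equate enrolling with signing consent, so the maximum of 380 is taken as the consented total.
- p = 60%, the assumed true AE proportion among those who are not screen failures.
- k = the number of screen failures: 1%, 2%, 5% or 10% of 380, that is 4, 8, 19 or 38.
- r = the AE proportion in screen failures divided by p: 0 (no recorded event) or 0.5 (gap events only).

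Reported proportion = [p × (380 − k) + r × p × k] / 380.

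| k | r = 0 | r = 0.5 |
|---|---|---|
| 0 | 60.0% | 60.0% |
| 4 | 225.6/380 = 59.4% | (225.6 + 1.2)/380 = 59.7% |
| 8 | 223.2/380 = 58.7% | (223.2 + 2.4)/380 = 59.4% |
| 19 | 216.6/380 = 57.0% | (216.6 + 5.7)/380 = 58.5% |
| 38 | 205.2/380 = 54.0% | (205.2 + 11.4)/380 = 57.0% |

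The relative loss is (k/380) × (1 − r) whatever p is. With p = 30% and r = 0, for instance, the range is 29.7% (k = 4) to 27.0% (k = 38). Removing screen failures from both numerator and denominator returns p in every row.

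**The case against.** The case for leaving Table 5 alone has real weight.

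- **The group may be close to empty.** Baseline SDMT, the dose and completion of M24 are all known from the parent trial and can be checked before consent. That leaves mainly the two exclusion criteria. This stands: 10% screen failures is an upper illustration, not a forecast, and with none the effect is zero.
- **A consent-based set matches consent-based AE collection.** Screen failures can add gap events as well as denominator. This also stands, and it is why the r = 0.5 column is shown. It softens the dilution. It removes it only if screen failures have the same recorded AE proportion as participants followed to M48.
- **Handling may be settled later.** Section 9.3 leaves final exclusions from any set to a decision before database lock, the Integrated Analysis Plan is not at hand, and the safety methods in Table 7 are redacted. An exposure-adjusted analysis therefore cannot be ruled out. But the set definition is stated in the protocol, and discretion without stated criteria does not correct it.
- **Little hangs on it.** The study is exploratory and single-arm, Table 7 lists no primary or secondary safety endpoint, and efficacy uses the FAS. This limits the weight of the point, not its correctness.

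Two stronger readings are tempting. A reader might infer that screen failures are never followed. The protocol is silent on their follow-up and expressly collects gap events after consent, so only the absence of a scheduled M36 or M48 visit can be read from it. A reader might also add screen failures on top of 380 and conclude that AE rates are materially understated. Under the protocol's own use of enrolment, 380 already counts everyone who consents, and no figure in the document supports a large number of failures.

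**Conclusion.** The point holds as a flaw of definition with a modest and uncertain effect. As written, Table 5 puts dosed screen failures into the denominator of every safety percentage, because its dose condition refers to treatment completed in another trial.

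The dilution of an assumed 60% AE proportion is 0.6 to 6.0 percentage points for 1% to 10% screen failures without events, and 0.3 to 3.0 points if they have half the AE proportion. It is zero if there are no screen failures. The lower end is the more plausible, since most eligibility facts are known before consent. These sizes rest on the assumed rates, on 380 consented, and on AE results being reported as simple percentages of the safety set. The SDMT and MSQoL-54 analyses are not touched.

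**What to change.** In Table 5, define the Safety Analysis Population as all members of the Screening Set who took one or more cladribine doses in CLARIFY MS and were not screen failures under Section 5.4. Three details matter:

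- Do not use enrolment as the dividing line. Sections 6.5 and 8.3.1 equate it with signing consent, so it would not separate screen failures.
- Keep anyone who entered follow-up, even if later found ineligible, and do not require a post-baseline safety assessment. Such a requirement would make inclusion depend on retention and could drop participants lost before M36.
- List any AE or SAE reported by a consented screen failure separately, so that no event is lost.

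The cost is one line in Table 5 and the matching line in the Integrated Analysis Plan, with no new data. AE percentages may become slightly less favourable, and screen-failure events would appear only in a listing and not in the summary tables.

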### 9.4 Statistical Analyses

The study is exploratory in nature. A control of the potential Type-I-error inflation caused by multiple endpoints and multiple testing is not implemented.

Parameter estimates with associated 95% confidence intervals will be reported, as applicable.

The study dataset comprises of multiple outcome assessments made for each participant over a 24-month period. Therefore, due to the longitudinal nature of the data and the lengthy follow-up period, it is likely that missing outcome data will be present due to loss to follow-up. Patterns

and degrees of missingness will be summarized and will trigger the approach to deal with missing data.

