#### 9.4.1 Efficacy Analyses

The efficacy analyses are described in [Table 6](#). All efficacy analyses will be performed on the FAS population.

**Table 6** Analysis of Efficacy Endpoints

Endpoint	Statistical Analysis Methods
Primary	
The proportion of participants with no decline or a maximal decline of 4 points in SDMT score at M48 will be described using a 95% confidence interval computed according to Wilson's score method.
 
A logistic regression with at least age and Baseline EDSS included as covariates will be performed as sensitivity analysis. Further factors or covariates to predict disease progression may be added as appropriate.
 
In order to investigate the robustness of results of the primary efficacy analysis with respect to missing values, additional sensitivity analyses will be conducted by applying multiple imputation techniques. The impact of different assumptions with regards to missing patterns will be investigated.

Secondary	
The differences in MSQoL-54 physical and mental health scores at M48 will be assessed using repeated mixed-effects linear regression, accounting for clinically relevant factors (e.g., age and EDSS), within-participant correlation, and pooled center correlation.
 
Estimates for the mean difference in scores between specified time points will be reported, with a 95% confidence interval and 2-sided p-value.

CCI	
CCI	
CCI	

Substance code: N/A

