#### 9.4.4 Sequence of Analyses

Final analyses will be performed at the end of study. In addition, interim analysis at extension study Baseline or M36 may be performed.

## 10

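### Does letting the observed missingness trigger the missing-data approach leave the primary SDMT percentage open to choice?

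*Protocol*

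**What the plan says.** Section 9.4 calls the study exploratory, expects outcome data to be lost through loss to follow-up, and says that patterns and "degrees of missingness will be summarized and will trigger the approach to deal with missing data".

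Table 6 in Section 9.4.1 describes the primary endpoint as a proportion with a 95% Wilson score interval. A covariate-adjusted logistic regression is a sensitivity analysis. For missing values, "additional sensitivity analyses will be conducted by applying multiple imputation techniques", and the effect of different assumptions about the missingness is to be examined.

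On the analysis set, Section 9.4.1 says "All efficacy analyses will be performed on the FAS population", and Table 5 says "The FAS will include all eligible participants". Eligibility requires only a parent-trial SDMT value (Section 5.1: "Have at least CLARIFY MS Baseline data on SDMT"), so a member of the Full Analysis Set (FAS) can lack the M48 value.

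The synopsis expects at most 380 enrolled and, after 10% to 20% drop-out, "it is expected to achieve a maximum of 300 to 340 evaluable participants for the extension study".

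Section 9 leaves the detail to the Integrated Analysis Plan, "which will be finalized prior to database lock". Section 9.4.4 adds that an "interim analysis at extension study Baseline or M36 may be performed".

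**The concern.** Two features look wrong on first reading.

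The first is the trigger sentence. A protocol that said nothing about missing data would simply be leaving the matter to the analysis plan. This one says that the observed missingness decides the approach, and it names no candidate methods, threshold or decision rule. The study is open label with one arm, the analysis plan need only be final before database lock, and an interim look is possible. M48 results could therefore be visible before the approach is settled.

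The second is the denominator. The efficacy analyses use all eligible participants, up to 380, while the synopsis speaks of 300 to 340 evaluable. Table 6 does not say whether the primary percentage is taken over everyone or over those with an M48 SDMT.

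The primary result is a single percentage with no comparator, so its reading depends heavily on what it is divided by. If that were picked after seeing the data, the reported figure could be a selected one, and a reader could not tell which version had been planned.

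**Working it through.** **Inputs.** From the synopsis: maximum enrolment 380, drop-out 10% to 20%, evaluable 300 to 340. From Table 6: a 95% Wilson interval. The documents give no expected share of stable participants; 80% is assumed here and varied from 50% to 90%.

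**The protocol's own figure.** 380 × 0.90 = 342 and 380 × 0.80 = 304. The protocol rounds these to 340 and 300. The evaluable count is enrolment less drop-out. It forecasts how many will have data and does not define a second analysis set.

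**Observed cases, 80% stable.** Wilson interval: [p + z²/(2n) ± z√(p(1−p)/n + z²/(4n²))] / (1 + z²/n), with z = 1.96.

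- 20% drop-out: 243/304 = 79.9% (75.1 to 84.1).
- 10% drop-out: 274/342 = 80.1% (75.6 to 84.0).

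**Extreme rules over all 380.**

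| Drop-out | Observed cases | Missing = decline | Missing = no decline |
|---|---|---|---|
| 20% | 79.9% | 243/380 = 63.9% (−16.0) | (243 + 76)/380 = 83.9% |
| 10% | 80.1% | 274/380 = 72.1% (−8.0) | (274 + 38)/380 = 82.1% |

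The favourable extreme stays inside the observed-case interval in both rows. The unfavourable one leaves it.

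**A less extreme departure.** If the missing group's stable share is lower by a gap g, the whole-set percentage falls by (missing fraction) × g. For g = 20 points:

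- 20% drop-out: (243 + 76 × 0.599)/380 = 75.9%, a fall of 4.0, inside 75.1 to 84.1.
- 10% drop-out: (274 + 38 × 0.601)/380 = 78.1%, a fall of 2.0, inside 75.6 to 84.0.

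**Gap needed to reach the lower limit.** (observed % − lower limit) × 380/missing:

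- 20% drop-out: 4.86 × 380/76 = 24.3 points.
- 10% drop-out: 4.55 × 380/38 = 45.5 points.

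The same calculation at other assumed shares gives, in points:

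| Assumed stable | 50% | 60% | 70% | 80% | 90% |
|---|---|---|---|---|---|
| 20% drop-out | 27.9 | 28.0 | 26.9 | 24.3 | 19.3 |
| 10% drop-out | 52.7 (not reachable) | 52.8 | 50.6 | 45.5 | 36.3 |

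Only at 90% stable with 20% drop-out does a 20-point gap pass the limit, and then barely: 90.1 − 4.0 = 86.1 against a lower limit of 86.3.

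**The passages side by side.** The trigger sentence closes a general paragraph on repeated outcome assessments and does not mention the primary proportion. It speaks of patterns of missingness; the primary row of Table 6 likewise plans sensitivity analyses under different assumptions about missing patterns. The natural joint reading is that the observed missingness shapes the assumptions of those sensitivity analyses, while the Wilson interval stays as the primary description.

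**The case for a change.** The best case for a change is that this is more than silence. The sentence ties the approach to study data, sits in the general part of Section 9.4 and so covers every outcome, and would bind an analysis plan that followed it faithfully. Multiple imputation in Table 6 tests the primary result but does not define it. At 20% drop-out the observed-case interval (75.1 to 84.1) and the missing-as-decline interval over 380 (59.0 to 68.6) do not overlap, and two or three sentences would close the question.

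Part of this stands. The sentence is loosely worded, its scope is not stated, and the visible primary row gives no status to a missing M48 SDMT.

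The rest does not carry. The trigger is the amount and pattern of missing data, not the SDMT results, so nothing in the text makes the choice depend on the outcome. Finalizing an analysis plan before database lock is common practice, and objecting to it in an open-label study is a general point rather than an error in this protocol. The non-overlapping intervals need a missing-as-decline rule that the protocol does not mention. The obvious replacement text, a Wilson interval on observed cases with multiple imputation beside it, is largely what Table 6 already provides. The choice of imputation covariates and of specific departures such as a delta adjustment belongs in the analysis plan.

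**Conclusion.** No change to the plan is called for. How a missing M48 SDMT counts in a descriptive proportion is detail that the Integrated Analysis Plan normally supplies, and Section 9 defers to that plan. The 380 and the 300 to 340 are consistent with each other. Followed as written, the protocol gives a descriptive percentage with a Wilson interval and tests it by multiple imputation under varied assumptions. There is no hypothesis test on the primary endpoint, so error rates are not at stake.

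At the protocol's 10% to 20% drop-out and an assumed 80% stable, a missing group 20 points worse moves the figure by 2.0 to 4.0 points, within its interval. Leaving the interval would take a gap of about 46 points at 10% drop-out or 24 at 20%. The choice matters mainly near the 20% end, and the planned sensitivity analyses address that case. The conclusion rests on the assumed stable share and on drop-out staying within the stated range. The analysis plan itself is not at hand. An analyst would sensibly report the number of FAS participants without an M48 SDMT beside the percentage, which the protocol already permits.

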#### 9.4.1 Efficacy Analyses

The efficacy analyses are described in [Table 6](#). All efficacy analyses will be performed on the FAS population.

**Table 6** Analysis of Efficacy Endpoints

Endpoint	Statistical Analysis Methods
Primary	
The proportion of participants with no decline or a maximal decline of 4 points in SDMT score at M48 will be described using a 95% confidence interval computed according to Wilson's score method.
 
A logistic regression with at least age and Baseline EDSS included as covariates will be performed as sensitivity analysis. Further factors or covariates to predict disease progression may be added as appropriate.
 
In order to investigate the robustness of results of the primary efficacy analysis with respect to missing values, additional sensitivity analyses will be conducted by applying multiple imputation techniques. The impact of different assumptions with regards to missing patterns will be investigated.

Secondary	
The differences in MSQoL-54 physical and mental health scores at M48 will be assessed using repeated mixed-effects linear regression, accounting for clinically relevant factors (e.g., age and EDSS), within-participant correlation, and pooled center correlation.
 
Estimates for the mean difference in scores between specified time points will be reported, with a 95% confidence interval and 2-sided p-value.

CCI	
CCI	
CCI	

Substance code: N/A

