#### Assessments related to CCI

should be done by the Investigator. It is not needed to have separate rater for neurological assessments.

Training modules are recommended for the sites about the assessments for sake of low inter-rater variability. Whenever possible, the same assessor should manage the same participant for these scales.

[figure not shown]
In addition, the Investigator will collect the participant's employment status. Procedures for the CCI and blood draws at the site are described in separate documents (CCI scan user's manual and the Laboratory Manual).

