## Study Administrative

### *Sponsor*

- The Sponsor of this extension study is Merck KGaA, [name].
- Sites, that participated in the CLARIFY MS trial, from Europe (including the following countries: Austria, Czech Republic, Denmark, France, Hungary, Italy, Poland, Slovakia, Spain, and the Netherlands) will be approached for participation in this extension study. About 65 sites are expected to participate.
- The Coordinating Investigator listed on the title page represents all Investigators for decisions and discussions on this study, per ICH Good Clinical Practice (GCP). The Coordinating Investigator will provide expert medical input and advice on the study design and execution and is responsible for the review and signoff of the clinical study report (CSR).

The study will appear in the following clinical studies registries: EU Clinical Trials Register, ClinicalTrials.gov, and national registries as per local regulations.

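### Is the primary Wilson interval too narrow because it ignores centre, while the secondary model in the same table allows for it?

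*Protocol*

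**What the plan says.** Table 6 in Section 9.4.1 of the protocol specifies that the primary proportion "will be described using a 95% confidence interval computed according to" Wilson's score method. No centre term is named. The same cell adds a logistic regression with at least age and Baseline EDSS as a sensitivity analysis, states that "Further factors or covariates to predict disease progression may be added as appropriate", and plans multiple-imputation analyses for missing values.

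The secondary row uses a repeated mixed-effects linear model for the MSQoL-54 scores, which is to account for clinical factors and for "within-participant correlation, and pooled center correlation".

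Section 9.4 declares the study exploratory, implements no control of Type I error, and says that "Parameter estimates with associated 95% confidence intervals will be reported, as applicable". Section 9 leaves further detail to an Integrated Analysis Plan, which is not at hand.

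On the number of centres, Appendix 2 (Study Administrative, Sponsor) states: "About 65 sites are expected to participate". It lists ten countries. On raters, Section 8.1 states: "Training modules are recommended for the sites about the assessments for sake of low inter-rater variability". The next sentence asks that, where possible, one assessor should stay with a participant for these scales.

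**The concern.** Wilson's interval rests on independent binomial outcomes. If participants at one site resemble each other more than participants at different sites, the variance of the overall proportion exceeds the binomial variance and a nominal 95% interval covers less often than 95%.

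Three features make this look like an oversight. The plan allows for centre correlation in a self-completed questionnaire but not in a performance test. The study spans about 65 sites in ten countries. Rater training is recommended, not required. Because the primary result is an estimate with an interval, an interval that is too narrow would overstate the precision of the main finding.

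**Working it through.** **Inputs from the protocol (Section 1.1 and Appendix 2).** The protocol expects that "up to a maximum of 380 participants will be enrolled into the extension study", with 10% to 20% drop-out, 300 to 340 evaluable participants and about 65 sites. The evaluable range reproduces: 380 × 0.90 = 342 and 380 × 0.80 = 304.

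**Inputs not in the protocol, assumed here.** Intraclass correlation (ICC) 0, 0.02 and 0.05; coefficient of variation (CV) of site size 0 and 0.8; true proportion 0.80.

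**Participants per site.** m = 300/65 = 4.62 and 340/65 = 5.23.

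**Design effect.** deff = 1 + ((1 + CV²) × m − 1) × ICC. The interval widens by about √deff. For sites regarded as random, approximate coverage is 2Φ(1.96/√deff) − 1.

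Example: CV 0, ICC 0.05, n = 300 gives 1 + (4.62 − 1) × 0.05 = 1.18, √1.18 = 1.09, coverage 92.9%.

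**Plain Wilson interval at 80%.** n = 300: 75.1% to 84.1%, half-width 4.5 points. n = 340: 75.4% to 83.9%, half-width 4.2 points.

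**Wilson interval recomputed at n/deff** (each range runs from n = 300 to n = 340):

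| CV | ICC | deff | √deff | approximate coverage, random sites | added half-width (points) |
|---|---|---|---|---|---|
| any | 0 | 1.00 | 1.00 | 95% | 0 |
| 0 | 0.02 | 1.07–1.08 | 1.04 | 94% | 0.2 |
| 0 | 0.05 | 1.18–1.21 | 1.09–1.10 | 92.5–93% | 0.4 |
| 0.8 | 0.02 | 1.13–1.15 | 1.06–1.07 | 93% | 0.3 |
| 0.8 | 0.05 | 1.33–1.38 | 1.15–1.17 | 90.5–91% | 0.7 |

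**Check by simulation.** Beta-binomial data were simulated with 65 equal sites, n = 320, proportion 0.80 and 40,000 runs. With sites random, Wilson coverage was 95.6% at ICC 0, 95.1% at 0.02 and 93.7% at 0.05. These values run slightly high because the binomial is discrete at a single n. Simulation over n = 300 to 340 gave about 94% at ICC 0.02 and 92.6% at 0.05, in line with the table. With the participating sites taken as the target, coverage at n = 320 stayed between 95.3% and 96.3% for ICC up to 0.10. Differences between sites do not by themselves make the interval too narrow; it also depends on which population is meant.

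**Does the table contradict itself?** The secondary row is worded as a model for scores at several visits, from which differences between time points are estimated. Random terms for participant and centre are natural there. The primary endpoint is one binary outcome per participant, summarised once. It is also built on the change from the participant's own CLARIFY MS Baseline, so a stable site or rater shift in SDMT level cancels in that change. Only site differences in the change itself would cluster the outcome, and the protocol gives no sign of these.

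**Does the rater passage support the concern?** The assessments it covers are redacted, and the adjoining text concerns neurological assessments, so it cannot be tied to SDMT. Its same-assessor request also works against rater drift within a participant.

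**The case for a change.** The strongest counter-argument is that the endpoint type explains the within-participant term but not the centre term: centre correlation is a separate source of variation and can affect a binary outcome too. The MSQoL-54 endpoints are also changes over time and still keep it. The protocol's purpose, to evaluate a treatment and inform future care, points beyond the participating sites, which favours a random-site view. Site sizes may well be unequal, since Section 4.1 aims at countries with at least 20 or sites with at least 10 parent-trial participants.

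Part of this stands. A centre-adjusted interval would be legitimate, and the direction of the effect is right for random sites with positive correlation. The size also depends on the assumptions. At ICC 0.10 with equal sites, coverage would be about 90% to 91%. If ten equal country-sized clusters were the relevant unit, even ICC 0.01 would give deff = 1 + (30 − 1) × 0.01 = 1.29 to 1 + (34 − 1) × 0.01 = 1.33, an interval 14% to 15% wider.

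None of these values comes from the documents, however. The sites are former CLARIFY MS sites chosen by parent-trial enrolment, not a random sample, so the fixed-site reading is as defensible as the other. The Wilson interval is not the only primary analysis planned either: the logistic model is open to further factors, and a centre-adjusted sensitivity interval is a detail that an analysis plan commonly supplies.

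**Conclusion.** The concern does not hold. The contrast between the two rows of Table 6 is real, but the plan states nothing wrong and does not contradict itself. Reasonable statisticians differ on whether a descriptive single-arm proportion needs a cluster-robust primary interval.

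For ICC 0.02 to 0.05, site-size CV up to 0.8 and a proportion of 80%, all assumed, the half-width would grow by about 0.2 to 0.7 percentage points from 4.2 to 4.5. With ICC 0, or with the participating sites as the target, no adjustment is needed. Larger effects require a higher correlation, more uneven sites or a few large clusters, for which the protocol gives no evidence. The visible text attaches no test, threshold or decision to the width, so within this range an added centre-adjusted interval would change no conclusion.
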